### **8.1.2 Study Conditions:**

***Untailored MMS Condition.*** Participants randomized to the untailored MMS condition will respond to two mobile phone text message prompts delivered on two days each week assessing hookah tobacco use and perceptions during the 6-weeks exposure period. After responding to the prompts, participants will immediately receive MMS messages with text and visual imagery communicating the risks of hookah tobacco use. MMS messages will be organized as a matrix by day and theme, and delivery scheduled such that prompts assessing hookah tobacco use and perceptions and messages conveying potential health harms, toxicant exposure, and addictiveness will be alternated with no two consecutive days repeating message themes and ensuring unique MMS content is delivered in each interaction. Message delivery will be based on data uploaded to the Mobile Commons system including preferred timing of delivery. Please see the attached message matrices for examples.

***Tailored MMS Condition.*** Baseline data from individuals randomized to the tailored MMS messaging condition will be uploaded to Mobile Commons to tailor MMS message content based on the following variables: 1) participants' preferred name and message delivery timing; 2) hookah tobacco use frequency (monthly versus weekly/daily); 3) beliefs and perceptions about the harms and addictiveness of hookah tobacco use. As with the untailored MMS condition, participants will respond to two text message prompts delivered on two days each day each week assessing hookah tobacco use and perceptions. Tailored MMS messages will be organized as matrices [58] by day, theme, and tailoring variable and uploaded in Mobile Commons. The matrices dictate the logic of branching tree structures that will be programmed to personalize message content based on baseline variables and dynamically during the intervention based on participants' reported hookah tobacco use, beliefs, and perceptions through the text messaging prompts. The system will capture participants' responses to text message prompts and using a preprogrammed algorithm will calculate a tailored MMS response based on the tailoring matrices. As in the untailored MMS condition, prompts assessing participants' hookah use and perceptions and MMS message themes will be scheduled such that no two consecutive days on which they are delivered will repeat message themes and unique MMS content will be delivered in each interaction. Our message tailoring approach is based on recommendations for the development of tailored interventions [58, 59] and prior studies [56, 60, 61]. The goal of the tailoring algorithm is to shift cognitive and emotional aspects of participants' perceptions of the harms and addictiveness hookah tobacco in order to motivate and achieve cessation based on behavioral change theoretical frameworks [58]. Please see the attached message matrices for examples.

***Control Condition.*** For those randomized to the control condition, after completing the baseline assessment, participants in the control condition will complete study assessments only and will receive no further messages.

**8.1.3 Follow-Up Assessments:** All participants will complete secure, confidential follow-up assessments online 6-weeks after baseline (Follow-Up 1), 3-months later (Follow-Up 2), and 6-months later (Follow-Up 3). Follow up assessments will be administered securely and confidentially online using Qualtrics in

the same manner as the baseline assessment described above. Participants will be emailed a personal survey link to complete follow-up assessments online. Measures administered will be similar to the baseline and designed to assess changes in hookah tobacco use behavior, beliefs, attitudes and perceptions.

#### **8.1.4. Measures**

The proposed measures for this study have all been validated and found to be reliable assessments across our studies and research by others. These measures follow recommendations for assessment of hookah tobacco use and related constructs. Baseline measures will assess demographics, motivation to quit hookah tobacco (9,10) and frequency of use in the past 30 days (9, 140) as the primary outcomes, as well as hypothesized mediators (9,10), moderators (9,10, 28,37), and potential covariates (4-6,21,28, 80,87,143,144-149). Follow-ups at 6-weeks (Follow-Up 1), 3-months (Follow-Up 2), and 6-months (Follow-Up 3) will measure similar outcomes. For details of measures to be implemented at each of these time points please see the attachments in Section 12.9.

**8.1.5 Study Retention & Follow-Up Procedures:** Assessment completion will be monitored in real time through Qualtrics and tracked in the study REDCap database by the Georgetown Lombardi study staff. The RA will conduct telephone/email follow-up with participants to ensure assessments are completed according to the protocol and to address any questions or challenges encountered. Participants will also be encouraged to contact research staff if they encounter any difficulties with study procedures. For the MMS conditions, message delivery and receipt will be recorded in real time in Mobile Commons and the RA will follow up by phone with participants as needed to provide technical support, resolve any problems, and bolster adherence. Participants will receive gift cards to acknowledge their time devoted to achieving study milestones: \$20 for baseline, \$25 for the 6-week and 3-month follow-up, and \$30 for completing the 6-month follow-up. Vanguard pilot participants will receive an additional \$10 gift card for each telephone interview completed. We have used these procedures in our research described above with good adherence to online and mobile messaging protocols and high prospective sample retention (Protocol 2014-1031).

#### **9 – Primary End Point**

Hookah tobacco use perceptions, beliefs, attitudes, and behavior.

#### **10 – Setting**

Study procedures will take place at the Georgetown Lombardi Comprehensive Cancer Center and Duke University.

#### **11. Multicenter**

Yes

#### **13. Local Accrual**

210

#### **14. Total Accrual**

420

#### **15. Duration of Accrual**

4 years

#### **16 – Duration of Study**

5 years

## 17 – Open Protocols

No

## 18- Sample Size

**Please provide a description of the statistical considerations (justifications for sample size or n, power or degree of change):**

Descriptive analyses will characterize study participants overall, by trial condition, and by study site, and will evaluate for assumptions of normality/equality of variance for continuous variables. Non-normal data will be transformed as needed. Bivariate analyses will examine if baseline covariates have non-trivial associations ( $p < 0.10$ ) with six-month outcome measures; those associated with outcome measures will be included in analyses as covariates. For Aim 1, since the primary outcomes are continuously measured variables at the 6-month follow-up (Follow-up 3), we will utilize an Analysis of Covariance (ANCOVA) model. The ANCOVA model will include the baseline covariates significantly associated with the outcomes of interest in the bivariate analyses and the stratification variables used for randomization. In exploratory analyses we will repeat this type of analysis for the 6-week and 3-month time points and also perform a longitudinal data analysis using mixed effects models [62] to examine if the effect of study condition (control versus combined MMS conditions) varies by time (a study condition by time interaction), controlling for any covariates associated with the outcome of interest. The primary outcomes and analytic approach for Aim 2 are similar to Aim 1, however we will compare differences in the 6-month outcomes across the control, untailored MMS, and tailored MMS conditions to evaluate the added effects of tailored messaging.

For Aim 3, we will draw from traditional mediation frameworks for preliminary analyses [63] and applying more robust methods to formally test for mediation [64]. We will also conduct exploratory analyses of MMS message dose effects in the untailored and tailored MMS conditions. After examining the distribution of message exposures and responses, we will explore dose effects in two ways: 1) dichotomized on whether a participant received less than or equal to or greater than the median MMS dose; and 2) as a continuous variable based on a count of total MMS messages delivered. Based on prior research [55], we will use ANCOVA and logistic regression to explore the potential effects of message dose on the primary outcome measures at 6-months controlling for any baseline variables that are associated with the message dose and the primary outcome measures.

We calculated statistical power to test our study hypotheses assuming a two tailed  $\alpha = .05$  and 80% sample retention at 6-months based on our ongoing and previous work. The power calculations were performed for 6-month outcome measures. For the continuous outcome variables, a baseline sample of 400 participants for the randomized trial (approximately 130 per condition and excluding participants from the vanguard pilot) with 80% retention at 6-month follow-up will provide 80% power to detect effect sizes smaller than Cohen's  $d = 0.37$  in analyses comparing the combined MMS conditions to the control condition for Aim 1. For the binary hookah tobacco cessation outcome, this sample will provide 80% power to detect differences in proportions such as 51% vs. 30% between any two conditions. For Aim 2, in analyses comparing continuously measured outcomes between any two conditions we will have 80% power to detect effect sizes smaller than Cohen's  $d = 0.43$ . For Aim 3, simulation studies provide estimated power to detect mediation effects using bias-corrected bootstrap analyses [65]. The sample will provide 80% power to detect medium indirect (i.e., coefficients in the range of 0.40) effects. Similarly, for analyses of the interaction between study condition and two-level moderators we will have 80% power to detect moderator effects smaller than Cohen's  $f = 0.22$ . These effect sizes are comparable to those observed in our recent work after a single exposure to messages online [35, 53].

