Participants in both MMS conditions will interact with the messaging system by responding to up to two text message prompts delivered to their personal mobile phones on two days each week during the 6-week exposure period (i.e., responding to up to a total of four text message prompts per week). Prompts will be delivered on two days each week based on the timing of participants' enrollment to target the timing and social contexts in which young adults use hookah tobacco [11]. The text message prompts will capture hookah tobacco use and cognitive and emotional aspects of perceived harm and addictiveness based on measures from our recent work [35, 53]. After responding to prompts, participants will immediately receive an untailored or tailored MMS message based on the conditions to which they are randomized. This dose of text message prompts and MMS messages is based on typical patterns of young adult waterpipe tobacco use (i.e., usually non-daily use) and recommendations for message dose in mobile behavior change programs to ensure sufficient exposure and avoid burnout over time [54-56]. Total MMS messages delivered to participants will vary depending on frequency of responses to the text message prompts, which will enable us to explore MMS message dose effects in analyses [55].

MMS messages will be sent and received using the software platform Mobile Commons [57]. Mobile Commons has an extensive track record supporting NIH and privately funded research and provides the technology backbone for the NCI's national SmokeFreeTxt program. Mobile Commons provides researchers with a user-friendly, secure platform to implement interactive mobile phone text and MMS messaging protocols. The platform features a content management system that allows for the creation of preprogrammed, automated schedules to send messages and collect responses without the need for technical programming. Messaging protocols are implemented as branching tree structures specifying the parameters for delivery of text message prompts, collection of participant responses, and triggers for message content delivered in return.

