**4. N/A**

**5. Please describe what will happen to the data if subjects decide to withdraw/dropout before study completion. Please include examples of reasons that may prompt subject withdrawal/dropout:**

We anticipate subject attrition to be 10% or less based on previous studies. Reasons for which subjects may drop out over the course of the study might include loss of interest in participating or lack of time to complete the procedures. Subject data collected prior to withdrawal will be analyzed.

**6. Please describe partial withdrawal and its safety implications:** Not applicable; withdrawal/partial withdrawal has no safety implications for participants.

**7. Potential Benefits:** While the direct benefits to participants are likely to be minimal, the findings of this study will be applied to inform future research and tobacco control efforts designed to reduce the population-level burden of tobacco-induced morbidity and mortality.

**8. Alternative to participating:** The only alternative is not participating.

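### No rule is stated for a missing 6-month outcome, and the model that could use lost participants' earlier visits is only exploratory in the protocol and absent from the SAP text; the likely bias is modest and the remedy cheap

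*Protocol*

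**What the plan says.** Protocol section 18 (Sample Size) sets the Aim 1 analysis at one visit: "since the primary outcomes are continuously measured variables at the 6-month follow-up (Follow-up 3), we will utilize an Analysis of Covariance (ANCOVA) model". Aim 2 uses a similar approach across the three conditions. Other visits have a lesser role: "In exploratory analyses we will repeat this type of analysis for the 6-week and 3-month time points and also perform a longitudinal data analysis", the latter by mixed-effects models that test whether the effect of condition varies over time.

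The same section bases power on "80% sample retention at 6-months based on our ongoing and previous work". Item 5 on withdrawal and dropout gives another figure: "We anticipate subject attrition to be 10% or less based on previous studies". It also contains the nearest thing to a missing-data rule: "Subject data collected prior to withdrawal will be analyzed".

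The SAP's statistical text, which is short and in the past tense, describes general linear models for risk appraisals and motivation to quit, rank tests for frequency of use, and logistic regression for cessation. The linear and logistic models are fitted visit by visit. It names no covariates and no mixed model. Neither document mentions imputation, a rule for unknown cessation status, an analysis set, or a missing-data sensitivity analysis.

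**The concern.** A single-visit ANCOVA, linear model, rank test or logistic regression uses only people whose outcome at that visit was observed, unless something is imputed. The item 5 sentence does not change this. Data from a participant who answered at 6 weeks and 3 months can be analysed in the tests at those visits, so the sentence is satisfied while that person is still absent from the 6-month estimate.

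This matters only if those who leave differ from those who stay in a way that is not balanced across arms. The documents make some imbalance plausible. The message arms have the burden of "responding to up to a total of four text message prompts per week", or 4 × 6 = 24 over the exposure period, together with imagery that section 9.3 admits may upset some people and staff calls to support adherence (section 8.1.5). By contrast, "participants in the control condition will complete study assessments only and will receive no further messages". Item 5 lists "loss of interest in participating or lack of time to complete the procedures" among the reasons for leaving. If early responders in one arm are more likely to stay, the 6-month completer contrast is shifted, in a direction that cannot be known beforehand.

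**Working it through.** **1. The plan's own figure.** Section 18 states 80% power at d = 0.37 for combined MMS against control, with 400 randomised and 80% retained. Retained per arm: 400 × 0.8 / 3 = 106.7 (or 130 × 0.8 = 104). At two-sided α = 0.05 the detectable effect is (1.96 + 0.842) × √(1.5/106.7) = 0.33, and power at 0.37 is 87–88%. The stated 80% is therefore conservative. It reproduces at α = 0.025 with 104 per arm: (2.241 + 0.842) × √(1.5/104) = 0.37. That mismatch is a separate matter. What counts here is that the matching calculation uses the retained number, which fits a completer analysis.

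**2. People who leave the 6-month result.** 400 × 0.20 = 80, or at most 400 × 0.10 = 40. For the 420 planned: 84 and 42.

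**3. Size of the bias (simulation).** From the documents: d = 0.37, 1:1:1 allocation (133 control, 267 MMS), loss of 20% or 10%. Assumptions: correlation 0.5 between any two visits; logistic dropout on the 6-week response with slope 0.5 or 1.0 per SD. Each pair below is slope 0.5 / slope 1.0. The likelihood column assumes that every lost participant has a 6-week value.

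| Dropout pattern | Unadjusted | Baseline-adjusted ANCOVA | Likelihood |
|---|---|---|---|
| 20% loss, link in MMS only | 0.42 / 0.46 | 0.39 / 0.41 | 0.37 / 0.37 |
| 20% loss, link in control only | 0.32 / 0.28 | 0.35 / 0.33 | 0.37 / 0.37 |
| Same link in all arms, 20% loss in each | 0.37 | 0.37 | 0.37 |
| Same link in all arms, 25% MMS and 10% control loss | 0.41 / 0.43 | 0.39 / 0.40 | 0.37 / 0.37 |
| 25% MMS and 10% control loss, unrelated to response | 0.37 | 0.37 | 0.37 |

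In the fourth and fifth rows the overall loss is (267 × 0.25 + 133 × 0.10)/400 = 20%. Standard errors at 20% loss are about 0.12 unadjusted and 0.10 for ANCOVA.

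- *10% loss, link in one arm group:* ANCOVA 0.38–0.39 or 0.35–0.36; unadjusted 0.40–0.41 or 0.32–0.35.
- *Correlation 0.3 or 0.7, 20% loss:* the ANCOVA shift stays at 0.02–0.04. The unadjusted shift is 0.03–0.05 at 0.3 and 0.07–0.12 at 0.7.
- *What the likelihood analysis can recover:* if half of the lost participants lack the 6-week value, it gives 0.38–0.39 or 0.35–0.36. If all lack it, it equals ANCOVA.

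**4. False positives under a true null.** With the steepest one-sided link, the ANCOVA bias of 0.044 against a standard error of 0.103 gives Φ(−1.96 + 0.43) + Φ(−1.96 − 0.43) ≈ 0.07. Simulation gives about 7% for ANCOVA and 11% unadjusted.

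**5. Cessation.** Assume section 18's 51% against 30% holds among completers, with 80% retained in both arms. Completers differ by 21.0 points. Counting missing as using gives 0.51 × 0.80 − 0.30 × 0.80 = 0.168, or 16.8 points. With 75% retained in the 51% arm and 85% in the other: 0.51 × 0.75 − 0.30 × 0.85 = 0.128, or 12.8 points. The completer standard error with 106 per arm is √(0.51 × 0.49/106 + 0.30 × 0.70/106) = 6.6 points.

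**6. Tipping point.** Shifting lost participants' values in one arm group by 0.1 SD moves the contrast by 0.02 at 20% loss. A result of 0.37 loses significance at a shift of (0.37 − 1.96 × 0.103)/0.20 = 0.84 SD. At 10% loss: (0.37 − 1.96 × 0.097)/0.10 = 1.80 SD.

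**The case against.** Four arguments on the other side have force.

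*The cited burdens suggest different loss rates, not a one-sided link to response.* This is right as far as it goes. Different rates unrelated to response do no harm (fifth row of the table), and no passage supports a link in one arm group only. But different rates combined with the same link in every arm still shift ANCOVA by 0.02–0.03 SD (fourth row). The bias is nil only if dropout is unrelated to response, or if both the mechanism and the loss rate are equal across arms.

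*The timing limits the remedy.* Prompts and images stop at 6 weeks, after which all arms have the same online surveys. Dropout caused by the messages would therefore fall mostly before or around the first follow-up, where a mixed model has no follow-up value to borrow. This stands and limits the gain.

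*Retention is actively managed.* Tracking, phone and email contact and a larger 6-month payment (section 8.1.5) should reduce the loss. They do not say how the remaining gaps are analysed.

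*The effect is small.* This also stands. The ANCOVA bias is under half a standard error, and the worst case needs the steepest slope tried in one arm group with none in the other.

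A reader might infer that the documents show differential dropout, or contradict themselves on its size. They do neither: the arm differences make it plausible only, and the 20% (6-month retention) and 10% (withdrawal or dropout) may measure different things.

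**Conclusion.** The concern holds at modest size. The rule for a missing 6-month outcome is not stated, and the sentence on withdrawn participants' data does not supply one. That lost participants leave the 6-month result is an inference from how these models work, supported by sizing the trial on the retained 80%. The absence of a mixed model is established only for the short SAP text supplied.

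At about 20% loss the expected distortion is 0.02–0.05 SD with baseline adjustment and 0.03–0.09 SD without it. The unadjusted figure is relevant because the SAP names no covariates. These sizes rest on the assumed correlation and dropout slopes.

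It would be too strong to conclude that the 6-month result is invalid or that power is lost. Section 18 already allows for the larger loss, and overturning an effect of 0.37 would need a one-sided shift of about 0.84 SD. It would also be too strong to expect a mixed model to repair everything. This is a worthwhile, inexpensive improvement.

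**What to change.** - **Risk appraisals and motivation to quit:** estimate the 6-month contrasts (control against combined MMS for Aim 1, pairwise for Aim 2) from a repeated-measures mixed model with arm by categorical time, baseline as covariate and unstructured covariance. Include everyone with at least one follow-up. Keep the completer ANCOVA as a sensitivity analysis, and add one tipping-point analysis that shifts lost participants' values in one arm group until the conclusion changes.
- **Cessation:** report the completer result beside missing counted as using. Multiple imputation is optional.
- **Frequency of use:** keep the rank test.
- **Reporting:** give retention by arm and visit, and the number without a 6-month value who have an earlier follow-up. That number decides what the mixed model can recover.

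The cost is a paragraph of SAP text and modest programming, with no new data. If the analysis is already final, as the SAP's past tense suggests, present these as labelled supplementary analyses and do not replace the primary. The downsides are reliance on missing at random, no contribution from people with no follow-up, and little gain if losses precede 6 weeks or retention is near 90%.

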## 19 – Importance/Value

Young adult hookah tobacco use is a critically important problem for tobacco control and cancer prevention [34]. Personally tailored message content can enhance the impact on cigarette smoking

cessation [41, 66], but this has not been tested for messages targeting hookah tobacco use. There is a critical need to adapt intervention strategies that have proven efficacy for cigarette smoking cessation to target factors known to influence young adults' waterpipe use [67]. Our study will test an innovative strategy for personalizing hookah tobacco message content by engaging in a two-way, interactive exchange where participant-generated data dynamically shape message content to enhance their impact.

## **9.2 – Risks**

This study does not involve drugs, devices, or medical procedures. The primary potential source of risks in this study is the risk of gathering behavioral information about tobacco use and viewing messages about the potential harms and addictiveness of tobacco use.

